STUDY PROTOCOL

Official Title: Targeting ADMA With Pioglitazone to Reduce Sympathetic Overactivity in CKD Patients

NCT Number: NCT03471117

Date: November 11, 2020

Study Rationale:

Chronic Kidney Disease (CKD) is a major health problem affecting more than 26 million Americans. An overactive sympathetic nervous system is a well known cardiovascular risk factor present in CKD. The increase in sympathetic nerve activity (SNA) may not only contribute to hypertension, but also accelerates the progression of end organ damage that is independent of any rise in blood pressure. Indeed, elevated SNA is associated with poor prognosis and increased risk of cardiovascular morbidity and mortality. Thus, the sympathetic nervous system constitutes a primary novel drug target needed for improving cardiovascular outcomes in CKD patients. However, limited effort has been directed at identifying the mechanisms driving sympathetic overactivity in CKD and importantly, SNA remains high in these patients despite standard drug therapy including angiotensin converting enzyme inhibitors and angiotensin II receptor blockers. Thus, if we could better understand the mechanism(s) of the elevated SNA, we should be able to devise more effective countermeasures and help reduce the subsequent morbidity and mortality among CKD patients. A potential signal driving SNA involves accumulation of the endogenous nitric oxide synthase inhibitor asymmetric dimethylarginine (ADMA). ADMA is elevated in CKD and is a strong, independent predictor of future cardiovascular events in these patients. Much of the work with ADMA has been correlational in nature with a focus on the well-known vascular endothelial properties of nitric oxide. However, increasing functional evidence indicates that nitric oxide is also a key signaling molecule involved in the tonic restraint of sympathetic outflow from the brainstem. Indeed, we recently demonstrated that systemic experimental inhibition of nitric oxide synthase causes sympathetic activation in healthy humans. In the current study, we will target the pathophysiological nitric oxide synthase inhibition caused by elevated ADMA concentrations in CKD and its role in mediating sympathetic overactivity. We will capitalize on the recent work indicating that thiazolidinediones reduce ADMA.

Recent work has reported that thiazolidinediones, such as pioglitazone, reduce ADMA likely by upregulating dimethylarginine dimethylamino-hydrolase (DDAH), the enzyme responsible for the breakdown of ADMA. Indeed, analysis of the DDAH gene revealed the presence of a thiazolidinedione binding site, implying that thiazolidinediones can directly regulate DDAH expression and subsequently ADMA levels. Thus, thiazolidinediones may provide a promising therapy in CKD. Indeed, in a recent study, CKD patients treated with pioglitazone were less likely to reach the composite end points of cardiovascular morbidity and mortality. Importantly, this effect was independent of the level of renal impairment suggesting protective effects even in moderate CKD. However, the mechanisms for these improvements remain unclear. In this study, we hypothesize that these favorable cardiovascular effects are through a lowering of ADMA and SNA. Thus, we will test the ability of pioglitazone to reduce ADMA and SNA in CKD patients.

Study Design:

We will perform a randomized, placebo-controlled crossover design study in CKD patients. Patients will be studied before and after one month of treatment with either placebo or pioglitazone (15 mg/day) with a 2-week washout period. Subjects will come to the research laboratory before and after the administration of either placebo or pioglitazone (15 mg/day) for one month. 20 CKD patients will be recruited and studied. Each visit will take approximately four hours.

VISIT 1: Prior to any screening/testing, all experimental measurements and procedures will be explained in detail and subjects will provide written, informed consent. A medical health history questionnaire will be filled out and women of child-bearing age will provide a urine sample for a pregnancy testing prior to any study procedures.

Subjects will be familiarized with the experimental measures and procedures prior to actual testing. The following measurements and procedures will be performed: Heart rate (ECG), blood pressure (Welch Allyn and finapres), respiratory rate (pneumobelt), brachial blood flow (duplex Doppler ultrasound), flow-mediated vasodilation, blood samples for metabolic and oxidative stress panel, muscle sympathetic nerve activity, handgrip exercise and cold pressor test.

In addition to laboratory BP measures, 24-hour ambulatory BP monitoring will be performed to better characterize BP fluctuations throughout the day and avoid any "white coat" influence on BP. After the baseline visit, subjects will be instrumented with this monitor that periodically measures BP (e.g., every 30 minutes) and asked to wear it for the next 24 hours. They will return the monitor within 2 days of completing the 24 hour

measurements. This device does not display the BP to the participant, it stores the BP data for downloading after returned to the lab. At the end of this visit, subjects will be given Pioglitazone or placebo pills for 1 month.

VISIT 2: This visit will be 1 month after visit 1. All experimental measures and procedures performed during visit 1 will be repeated. If the subjects received placebo treatment at the end of visit 1, they will receive pioglitazone pills at the end of visit 2, or vice versa. Subjects will be sent home with a 24-hour ambulatory BP monitor.

VISIT 3: This visit will be 2 weeks after visit 2. Same experimental measures and procedures performed in visit 1 and 2 will be repeated. Subjects will be sent home with a 24-hour ambulatory BP monitor.

Experimental Measurements and Procedures:

Anthropometrics: We will measure each subject's height, using a standard stadiometer, and weight, using a balance or digital scale. Waist and hip measurements will be taken using a measuring tape.

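### The Study Design calls for measurement before and after one month of treatment with a 2-week washout, but the visit plan sets the last measurement only 2 weeks after the second treatment is handed out

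*Protocol*

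**What the plan says.** The Study Design section of the Protocol names a randomised, placebo-controlled crossover and sets its timing: "Patients will be studied before and after one month of treatment with either placebo or pioglitazone (15 mg/day) with a 2-week washout period". The aim, at the end of the Study Rationale, is: "Thus, we will test the ability of pioglitazone to reduce ADMA and SNA in CKD patients".

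The visit plan in the same section then runs as follows.

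- **Visit 1**, after the baseline measures: "At the end of this visit, subjects will be given Pioglitazone or placebo pills for 1 month".
- **Visit 2**: "VISIT 2: This visit will be 1 month after visit 1". All measures are repeated and the treatments are switched. Of patients who had placebo first, it says "they will receive pioglitazone pills at the end of visit 2, or vice versa".
- **Visit 3**: "VISIT 3: This visit will be 2 weeks after visit 2". All measures are repeated once more.

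Nothing is scheduled after Visit 3, and the Blood draw paragraph counts three visits in total. The washout is named only in the opening of the Study Design. The visit plan mentions none and gives no instruction to delay the second pills.

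**The concern.** A crossover compares each patient on one treatment with the same patient on the other, so it needs a measurement at the end of each treatment. Visit 2 supplies the first. Visit 3 is the only visit that could supply the second, and on its stated date it cannot do so.

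What is at stake is the comparison that answers the aim. Staff who follow the visit plan would not run the design described at the start of the same section. A reader of the results could not tell whether Visit 3 is a value part-way through the second treatment or a value off treatment. This cannot be left to an SAP: visit dates, treatment length and washout are fixed in the Protocol, and no analysis can supply a measurement that was not taken.

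**Working it through.** **Inputs.** One month per treatment and a 2-week washout (Study Design). Visit 2 at 1 month, second treatment handed out at its end, Visit 3 at 2 weeks after Visit 2 (visit plan). Three visits in total (Blood draw). 20 patients (Study Design). The visit plan does not give the length of the second supply; one month comes from the Study Design. Assumption: 1 month = 30 days, checked over 28 to 31.

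**Step 1: the plan's own dates.** Visit 1 is day 0, Visit 2 is day 30, and Visit 3 is day 30 + 14 = 44.

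**Step 2: end of the second treatment, counted from Visit 2.**

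| | Month of 30 days | Month of 28 to 31 days |
|---|---|---|
| With washout | 14 + 30 = 44 days | 42 to 45 days |
| Without washout | 30 days | 28 to 31 days |
| Allowed by the visit plan | 14 days | 14 days |

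Visit 3 therefore falls 44 − 14 = 30 days, or 30 − 14 = 16 days, before that point. No month length closes the gap.

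**Step 3: the possible readings.**

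- *Second pills start at Visit 2.* There is no washout. Visit 3 comes at 14/30 = 47% of the month (45% to 50% for months of 31 to 28 days). Pioglitazone is measured after about 30 days in one sequence and 14 in the other, so length of exposure is confounded with period. In patients given pioglitazone first, the placebo value comes 14 days after the last pioglitazone dose, against 14 + 30 = 44 days under the Study Design, so carryover is possible.
- *The 2 weeks are the washout.* Visit 3 comes before the second treatment and no measurement follows it. Each patient is measured on one treatment only. With 1:1 allocation (assumed, not stated), about 10 of 20 have no value on pioglitazone and the other 10 none on placebo.
- *The second period is meant to last 2 weeks.* This contradicts the one month in the Study Design and still leaves no washout.
- *The hand-out sentence belongs under Visit 3.* There is then still no visit after the second treatment.
- *Each patient gets one treatment only.* The Visit 2 text gives every patient the other one.

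**Step 4: size, if pills start at Visit 2.** Let c be the share of the pioglitazone effect still present 14 days after stopping, and f the share reached after 14 days on it. Visit 2 minus Visit 3 is (1 − c) × effect + period in patients given pioglitazone first, and −f × effect + period in the others. Half the difference is (1 − c + f)/2 × effect. The Protocol gives neither c nor f. Letting each run from 0 to 1 covers everything from none to all of the effect, so no figure is offered.

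**Step 5: size, if the second treatment is never measured.** Assume 10 patients per sequence, equal variances s², and equal correlation ρ (0 to 1) between visits.

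- Complete crossover: variance = s²(1 − ρ)/10.
- Visit 2 groups, unadjusted: 2s²/10; ratio 2/(1 − ρ), at least 2.
- Visit 2 groups, adjusted for Visit 1: 2s²(1 − ρ²)/10; ratio 2(1 + ρ), at least 2.

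These are large-sample formulas. With 10 per group the adjustment slope is itself estimated, which raises the ratio: simulation gives 2.1, 3.3 and 4.1 at ρ = 0, 0.5 and 0.9, against 2, 3 and 3.8 by formula. The lower limit of 2 therefore holds at this size; no upper limit is claimed.

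**The case against.** The strongest reply is that this is a slip in one sentence. The washout and the Visit 3 interval are both 2 weeks, so one figure may have been put where another belonged. If the trial ran to the Study Design, the harm is confined to the text. That stands as a possibility, but the text does not show which item is wrong.

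Several stronger readings are tempting and are not supported.

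- *That the Study Drugs section is contradicted too.* It says how long the drug is taken, not when patients are measured. Nothing says that the second pills stop at Visit 3, so a full month of dosing remains possible. For the same reason Visit 3 cannot be taken as the end of participation. If the 2 weeks are the washout, dosing could match the Study Design entirely, with only the final measurement absent.
- *That three visits are in themselves too few.* A separate baseline for each treatment would need four measurement points, but three visits could serve with one shared baseline. The firm conflict is the date of the last measurement.
- *That Visit 3 could serve as a clean off-treatment value to sharpen the Visit 2 comparison.* That would require no carryover 14 days after the first treatment, which the Protocol does not establish. If carryover remains, Visit 3 is affected by the randomised first treatment, and adjusting for it would bias the comparison.

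**Conclusion.** The contradiction is certain on the text: the Study Design needs about 44 days from Visit 2 to the end of the second treatment, or 30 without a washout, and the visit plan allows 14. No reading considered here removes it.

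Its effect on the results is not certain. It depends on which item is wrong and on what was done, neither of which the Protocol shows. A reader might infer that the crossover estimate is biased by some known amount, or that precision is lost by a fixed factor. Neither follows. The only figure that holds is conditional: if the second treatment is never measured, the Visit 2 comparison has at least twice the variance of the complete crossover, assuming 1:1 allocation, equal variances and equal correlations from 0 to 1. The passages must be reconciled because the visit plan as written does not deliver the stated comparison.

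**What to change.** Reconcile the opening of the Study Design with the visit plan, and the Blood draw paragraph if a visit is added, so that treatment length, washout and the timing of the last measurement agree. Which schedule is right is for the sponsor to decide.

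If the three-visit plan as written is what runs or has run:

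- state that the only one-month randomised comparison is between groups at Visit 2;
- do not present Visit 3 as a measurement after one month of the second treatment;
- label Visit 3 with its actual exposure, and with possible carryover from the first treatment whether or not the second had started.

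**Cost.** If Visit 3 was misdated, or if the plan stands, the change is wording. If the plan stands, the stated comparison is also less favourable, being between groups. If the sponsor finds that a fourth visit was intended, the Protocol's own figures ("20 CKD patients will be recruited and studied" and "Each visit will take approximately four hours") give 20 × 4 = 80 further laboratory hours, and its blood limit allows up to 150 mL more per patient.

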Sympathetic Nerve Activity: A tiny microelectrode will be placed in the peroneal nerve of the leg, located just below the knee on the outer part of the leg. Alternatively, the median nerve located in the upper arm will be used. At these points the nerves are closest to the surface of the skin. The course of the nerve will be determined by electrically stimulating through the skin with a pencil shaped electrode. When the nerve is stimulated, involuntary twitching and/or tingling sensations of the foot or hand will occur. The twitching or tingling will disappear when the stimulation is stopped. Once the nerve is found, two tiny, sterile,

microelectrodes will be inserted through the skin. One is a reference electrode placed just above the nerve site (2 cm) and the other is the recording electrode. The recording electrode is advanced into the nerve. When the tip of the electrode enters the nerve, the subject may briefly notice either pressure or tingling sensations. At this point, minor adjustments in the position of the electrode will be made until an optimal nerve signal is obtained.

Peripheral Blood Flow: Blood flow will be determined by using pulsed Doppler ultrasound to non-invasively measure mean arterial blood velocity and diameter. Peripheral blood flow (e.g., femoral artery, brachial artery) can be obtained by placing a Doppler flow probe on the surface of skin over the respective artery. For Doppler ultrasound measurements, when requested by the participants for comfort purposes, an individual of the same sex will be present to conduct these measurements during the protocol. Ultrasound imaging of artery diameter will be performed at a site matching that at which velocity is measured. The following formula is used to calculate blood flow: $\pi \times (\text{artery radius})^2 \times \text{velocity}$.

Baseline measurements (such as heart rate, blood pressure, blood flow) will be recorded during 10-20 minute supine rest. After baseline measures, experimental procedures listed below will be performed. All procedures will be explained in detail verbally to the subject during consenting. The FDA approval status for all the devices used in this protocol is provided in an attached document.

Flow mediated dilation (FMD): Endothelial function will be assessed via flow mediated dilation (FMD) which includes inflating a blood pressure cuff above the participant's systolic blood pressure for 5 minutes, and making continuous blood flow measures before and after the release of the blood pressure cuff. This will be performed on a peripheral artery (e.g., brachial artery, popliteal artery).

Handgrip Exercise and Post-Exercise Ischemia: Subjects will perform handgrip exercise using a hand dynamometer with their arm supported on an adjustable bedside table. Handgrip exercise will be performed for either three minutes or until they feel like they cannot maintain the exercise (i.e., fatigue). Five seconds before stopping the exercise, a cuff around the upper arm will be inflated to impede blood flow for up to three minutes. This traps the metabolites that were produced during exercise in the area of the muscle, which maintains stimulation of skeletal muscle metaboreceptor afferents. Since these metaboreceptor afferents contribute to the rise in blood pressure during exercise, continued stimulation of these receptors maintains a blood pressure response.

Cold Pressor Test: The subject will be asked to place their hand in ice water for 2 minutes. This procedure will be used to cause transient increases in heart rate and blood pressure.

24-hour ambulatory blood pressure: After each visit, subjects will be instrumented with a 24-hour ambulatory blood pressure monitor that measures blood pressure every 30 minutes. The device does not display blood pressure to the subject but stores the data for downloading after returned to the lab (2 days after completion of 24 hour measurements). This is performed to better characterize BP fluctuations throughout the day and avoid any "whit coat" influence on BP.

Study Drugs:

Pioglitazone is in a class of anti-diabetic drugs called thiazolidinediones that are primarily used in the treatment of type 2 diabetes. We aim to determine if this drug also reduces ADMA and SNA in CKD patients. This drug will be taken orally as a pill or capsule for one month. The dosage is 15 mg/day. This is on the lower dosage side for pioglitazone with the maximum dosage being 45mg/day. The study will utilize a randomized, crossover placebo-controlled study design. The randomization for study drugs will be carried out by research personnel. The research subject is not responsible for the cost of the drug or for drug administration costs.

Placebo pills: Placebo will consist of sugar capsules of similar color and appearance as Pioglitazone pills.

INCLUSION CRITERIA: We will study CKD patients classified as Stage 3 and 4 of National Kidney Foundation Classification with estimated GFR between 15 and 59 mL/min/1.73 m² according to the Modification of Diet in Renal Disease (MDRD) formula based on serum creatinine, age, gender, and race. Men and women 35 to 70 years of age will be studied.

EXCLUSION CRITERIA: We will study patients on their existing drug therapy.

Exclusion criteria include: 1) allergy to Glitazones 2) myocardial infraction 3) heart failure 4) angina 5) history of kidney stones 6) liver disease (abnormal liver enzymes) 7) anemia (hemoglobin <8 g/dl) 8) cancer with current treatment 9) previous organ transplantation 10) immunosuppressant therapy 11) human immunodeficiency virus infection 12) pregnancy or lactating 13) current tobacco use 14) Dilantin and oral contraceptive usage due to potential drug interaction with glitazones and 15) self-identified history of hypoglycemia.

References:

Patient population: Hypertensive patients

Drug and dose used: Pioglitazone, 30 mg/day

Period of use: 12 weeks

Adverse effects reported: none

Change in glucose: significantly decreased glucose (from 6.4 to 5.9 mmol/dL)

Patient population: Hypertensive patients

Drug and dose used: Pioglitazone, 30 mg/day

Period of use: 6 months

Adverse effects reported: Mild leg edema

Change in glucose: no significant decrease in fasting blood glucose

3) **Dana E. King, Marty Player, Charles J. Everett.** The impact of pioglitazone on ADMA and oxidative stress markers in patients with type 2 diabetes. *Primary Care Diabetes* 6: 157-161, 2012.

Patient population: Type 2 Diabetes

Drug and dose used: Pioglitazone, 30 mg/day

Period of use: 12 weeks

Adverse effects reported: None

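### Does handing out pills just before the 24-hour blood pressure recordings leave the Visit 1 and Visit 2 recordings in the wrong treatment state?

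*Protocol*

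**What the plan says.** Under Study Design, the intended comparison is: "Patients will be studied before and after one month of treatment with either placebo or pioglitazone (15 mg/day) with a 2-week washout period".

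For Visit 1, the protocol puts the ambulatory recording after the visit: "After the baseline visit, subjects will be instrumented with this monitor that periodically measures BP", and patients are "asked to wear it for the next 24 hours". The dispensing sentence for the same visit reads "At the end of this visit, subjects will be given Pioglitazone or placebo pills for 1 month".

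For Visit 2, patients who had placebo first are told that "they will receive pioglitazone pills at the end of visit 2, or vice versa", and all patients go home with the monitor. Visit 3 is placed as follows: "This visit will be 2 weeks after visit 2". The section on 24-hour ambulatory blood pressure gives the general rule: "After each visit, subjects will be instrumented with a 24-hour ambulatory blood pressure monitor that measures blood pressure every 30 minutes".

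The Study Drugs section gives a daily amount and a duration of one month, but no clock time and no rule for first or last doses. It states the aim as: "We aim to determine if this drug also reduces ADMA and SNA in CKD patients".

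**The concern.** Each of the first two recordings begins when the patient already has the next supply in hand. If a pioglitazone-first patient takes a pill on the evening of Visit 1, part of the baseline recording is on drug. At Visit 2 the recording is meant to describe the end of period 1. It could instead fall on the first day of the second treatment or, if the washout begins there, on the first day off treatment.

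Any real drug effect on ambulatory pressure would then tend to be diluted, in a study of only 20 patients. An analyst could not repair this afterwards if pill times had not been collected. Ambulatory monitoring is also the measure brought in to remove the influence of the clinic setting on blood pressure, so its timing deserves a check.

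**Working it through.** The protocol gives no figure on this point to reproduce. The check is a timeline, a count of the recordings that could be affected, and an expression for the possible dilution.

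**Timeline.** A recording lasts 24 hours with a reading every 30 minutes, so 24 × 2 = about 48 readings. All of them come after the hand-out. With no stated pill time, anywhere from 0 to about 48 readings could follow a first new pill.

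Now ask whether the text allows a consistent reading of period 1. Assume one pill a day, a supply of D pills, Visit 1 on day 0 and Visit 2 on day D.

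- First pill on day 0: the last pill falls on day D − 1, the day before Visit 2.
- First pill on day 1, after the Visit 1 recording has finished: the last pill falls on day D, the day of Visit 2.

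Under the second reading the Visit 1 recording is untreated, and the last period-1 pill falls on the day the Visit 2 recording begins. The protocol neither requires nor excludes this reading. It is shown only to establish that the sentences are compatible for period 1, and the choice rests with the sponsor.

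**Count.** 20 patients × 3 visits = 60 recordings. Let n be the number randomised to pioglitazone first. The allocation ratio is not stated, so take n = 10, with a range of 8 to 12. Visit 3 is left out because no pills are handed out there.

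| Event at Visit 2 | Recordings whose active-drug state could differ from intent | n = 8 | n = 10 | n = 12 |
|---|---|---|---|---|
| Second treatment starts at once | n (Visit 1) + 20 (Visit 2) | 28 | 30 | 32 |
| Washout starts | n (Visit 1) + n (Visit 2) | 16 | 20 | 24 |

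These are ceilings. They suppose that every patient who could take a pill, or stop one, at an unhelpful moment does so.

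**Dilution.** Let D* be the one-month drug effect on ambulatory pressure, f the share of it present in the first 24 hours on drug, and g the share lost in the 24 hours after Visit 2.

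- Change from Visit 1 to Visit 2, pioglitazone first: (1 − g)D* − fD*.
- Same change, placebo first: fD* if the second treatment starts at once, 0 if washout starts.
- Difference between sequences: (1 − g − 2f)D* or (1 − g − f)D*.

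The loss is therefore g + 2f or g + f, and it is zero when f = g = 0. The protocol supplies neither f nor g. It treats for one month, and the three pioglitazone studies in its reference list ran for 12 weeks, 6 months and 12 weeks, so nothing in it points to a first-day effect. The expression also describes only a between-sequence comparison in period 1, not the within-patient crossover comparison the design is built on. No percentage from it is carried into the conclusion.

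**What is not touched.** Blood sampling, nerve recording and laboratory pressure take place during the visit, before that visit's pills are given out. ADMA and sympathetic nerve activity, the two stated targets, are outside the reach of this point.

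**The case for a change.** The best argument for a change is that this is a conduct instruction and not an analysis detail. No SAP can recover pill times that nobody wrote down, and a null ambulatory result could then not be told apart from mistimed recordings. Clarifying the wording and noting two times at each changeover would cost little. Settling the washout question would still leave the Visit 1 baseline recording open.

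The factual part of this stands: the protocol does not say how dosing relates to the recording window. What does not follow is that a wrong result is in prospect. The Visit 1 remainder is whether one daily pill falls inside one 24-hour window, in pioglitazone-first patients only, for a supporting measure. The before-and-after intent already tells staff what that recording is for.

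The Visit 2 part depends mainly on a different issue. A 2-week washout, crossed-over pills given at Visit 2 and a Visit 3 only two weeks later do not fit together with a full month of second treatment. Those passages must be reconciled for the sake of every endpoint, and defining the changeover would settle most of what is raised here. When that is done, a line relating each recording to dosing, and a note of the pill times, would be a sensible courtesy.

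Analysing each recording by the treatment actually taken would not be a plain improvement. It replaces randomised assignment with what happened after randomisation, and that choice usually belongs in the SAP, which was not available.

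**Conclusion.** No change is needed on this point by itself. It is an unwritten operational detail that trial staff can fill sensibly from the stated intent, not a plan to record blood pressure in the wrong treatment state. At most 20 or 30 of 60 recordings could be touched with 10 patients per sequence (16 to 24, or 28 to 32, with 8 to 12 in the pioglitazone-first sequence). All of them are ambulatory recordings at Visits 1 and 2. The effect on results cannot be sized from the protocol and may be nil. This conclusion rests on once-daily intake, on pills being handed out after the in-visit measurements, and on the conflict over washout, Visit 2 dispensing and Visit 3 timing being handled as the separate matter it is.
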